## ABSTRACT

**Background:** The Procalcitonin Antibiotic Consensus Trial (ProACT) is a multicenter randomized trial designed to determine the impact of a procalcitonin antibiotic prescribing guideline, implemented with basic reproducible strategies, in US emergency department (ED) patients with lower respiratory tract infection.

**Objective:** To provide the a priori trial statistical analysis plan.

**Methods:** The ProACT trial is a patient-level randomized, multicenter, prospective, parallel-arm clinical trial. A total of 1,664 patients were randomly allocated 1:1 to either the procalcitonin guided arm or usual care. The primary outcome measures are total antibiotic days and a composite adverse outcome endpoint by Day 30. Secondary outcomes and other measured data are declared. Key trial design components are highlighted. Methods for statistical analysis are described, including the primary analysis method, secondary and sensitivity analyses, plan for handling missing data, and accounting for non-compliance. Intervention effect will be evaluated in pre-specified subgroups.

**Discussion:** Our analysis plan set in advance limits bias in data analyses and reporting of results.

**Trial registration:** This study was registered at ClinicalTrials.gov, NCT02130986, on May 1, 2014.

## I. OVERVIEW

### BACKGROUND AND GOALS

Antibiotic prescribing is a common medical decision-making problem. Clinicians over prescribe antibiotics for fear of untreated bacterial illness, contributing to antibiotic overuse [1, 2] and resistance [3, 4]. This pattern is common in suspected lower tract respiratory infection (LRTI), where distinguishing bacterial from viral etiologies is challenging. As a marker for bacterial infection [5-7], several European trials found that procalcitonin-guided care may safely reduce antibiotic use in LRTI [8-11]. However, applicability to United States (US) practice is unclear[12]. Current recommendations for procalcitonin guided LRTI care vary from strong support to discouraging routine adoption [13-15].

The Procalcitonin Antibiotic Consensus Trial (ProACT) is a patient-level randomized, multicenter, prospective, parallel-arm trial to assess the effects of a procalcitonin guideline (implemented with basic reproducible strategies) on antibiotic exposure and adverse outcomes in patients managed for a clinically diagnosed LRTI in a U.S. emergency department. The University of Pittsburgh institutional review board (IRB) approved the design. The trial is registered with ClinicalTrials.gov (NCT02130986). Further details about the study rationale, design, and implementation are reported elsewhere [16].

The aim of this paper is to present the statistical analysis plan for the ProACT trial. We finalized the plan before treatment assignment was unblinded.

## PATIENT POPULATION

From 14 EDs in the US, we enrolled adults with a primary clinical diagnosis of acute LRTI. Detailed inclusion and exclusion criteria were previously reported [16] and are summarized below.

### Inclusion criteria

Enrolled patients were at least 18 years of age, with a primary clinical diagnosis of acute LRTI (as per the treating clinician), and treated by a clinician willing to consider procalcitonin in antibiotic decision-making.

### Exclusion criteria

Patients with conditions where (1) physicians are unlikely to withhold antibiotics (e.g., endotracheal ventilation), (2) procalcitonin can be elevated without bacterial infection (e.g., recent surgery), or (3) follow-up would be difficult (e.g., prisoners, homeless) were excluded.

## STUDY HYPOTHESES

We will sequentially test the following null hypotheses:

- H10: Procalcitonin guideline implementation does not reduce antibiotic exposure by Day 30.
- H20: Procalcitonin guideline implementation increases the proportion of subjects who experience a composite endpoint of adverse outcomes by Day 30, by  $\geq 4.5\%$ . (noninferiority)

In the final analyses, we will also test a more conservative null hypothesis:

- H10: Procalcitonin guideline implementation does not reduce or increase antibiotic exposure by Day 30.

## II. MEASURES

### PRIMARY OUTCOMES

Our primary outcome (Aim 1) is total antibiotic exposure, defined as the total number of antibiotic-days by Day 30. An antibiotic-day occurs when a patient receives any oral or intravenous antibiotics, excluding antibiotics given for non-infectious indications (e.g. rifaximin for hepatic encephalopathy) and antivirals. We will determine the total number of antibiotic-days by Day 30 by combining the number of antibiotic-days from ED or hospital admission to discharge, with the number of antibiotic-days from discharge to Day 30 (obtained by phone calls at Day 15 and Day 30, and from any rehospitalization up to Day 30). Our primary safety outcome (Aim 2) is a combined endpoint of adverse outcomes that could result from withholding antibiotics in LRTI. The composite endpoint consists of death, septic shock (vasopressor use), mechanical ventilation via endotracheal tube, renal failure (Kidney Disease: Improving Global Outcomes stage 3 – new renal replacement therapy, tripling of baseline creatinine, or serum creatinine  $\geq 4.0$  mg/dL [17]), lung abscess/empyema, development of pneumonia in non-pneumonia LRTI, and hospital readmission. The primary safety outcome is reached if at least one of these outcomes occur by Day 30. We will also examine each adverse outcome individually. We will determine if these outcomes have been reached by Day 30 by combining outcome occurrences from ED or hospital admission to discharge, with outcome occurrences from discharge to Day 30 (obtained by phone calls at Day 15 and Day 30, and from any rehospitalization up to Day 30).

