Questions of generalizability and safety preclude widespread application. In these trials, a senior investigator potentially influenced ED staff by directly providing procalcitonin guideline advice. In ProHOSP, “enforcement” was accomplished by requiring physicians to follow Web-based instructions before registering their patient in the study. Physicians could only overrule the guideline after consulting the coordinating center. In routine US practice, neither method is ideal nor practical. Senior investigator influence threatens generalizability and direct interference with physician decision-making is counter to practice norms. US physician and patient expectations also likely differ from their Swiss counterparts and will require contemporaneous, individual data to alter. Further, only ProHOSP was powered to test safety. ProHOSP found no difference between groups in a composite adverse outcome endpoint, but used a relatively large non-inferiority margin. Their combined endpoint included an adverse outcome already potentially present at enrollment and subject to non-physiologic factors such as bed availability (ICU admission). The authors also observed in the procalcitonin arm a slightly higher mortality rate and did not report outcomes past 30 days.

C. TRIAL DESIGN

We propose a patient-level randomized trial to test an evidenced-based implementation strategy of a novel procalcitonin antibiotic guideline for LRTI. We will test the impact of serial procalcitonin measurement on total antibiotic exposure by Day 30. ProACT is powered to demonstrate safety with a 4.5% non-inferiority margin for a combined adverse event endpoint of the primary concerns of withholding antibiotics, and to detect a reduction of ≥ 1 antibiotic-day. We will enroll all LRTI as initial clinical presentations, embracing the clinical overlap that exists in practice and to optimize enrollment.

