Participants in the procalcitonin group will have one teaspoon of blood drawn for a procalcitonin level (\leq one hour after randomization goal) in the ED, and if hospitalized, 6-24 hours after the initial ED blood draw, and on Days 3, 5, and 7. Days 3, 5, and 7 blood draws for procalcitonin will only occur in hospitalized patients on antibiotics and/or at the treating clinician's discretion. For the purpose of this study, time zero is at randomization and Day 1 is defined as time of enrollment through 11:59PM of the same day.

In the ED, we will quickly (<1 hour goal) provide clinicians the procalcitonin result, accompanied by the procalcitonin antibiotic guideline (provided below). For participants who have not yet received antibiotics, we will ask the clinician to consider waiting for the procalcitonin result.

For patients admitted to hospital (or to an observation unit), we will inform the hospital clinician of the ED procalcitonin result, and that serial procalcitonin levels will be obtained, including a second one in 6 - 24 hours after the initial ED blood draw. During the hospital stay, study staff will inform clinicians when new serial procalcitonin results are available. The same procalcitonin guideline will be provided with both the initial and serial procalcitonin measurements - withhold or cease antibiotics if low, administer or continue if high.

Procalcitonin antibiotic guideline

Procalcitonin level (μ g/L)	Bacterial etiology	Recommendation
< 0.1	Very unlikely	Antibiotics strongly discouraged ¹
0.1 - 0.25	Unlikely	Antibiotics discouraged ¹
> 0.25 - 0.5	Likely	Antibiotics recommended ²
> 0.5	Very likely	Antibiotics strongly recommended ²

1. Initial antibiotics can be considered for critical illness, Legionella pneumophilia. Procalcitonin should be evaluated in context with all findings and the total clinical status; clinical judgment always necessary.

2. For outpatients, antibiotic duration based on level ($> 0.25-0.5 \mu$ g/L:3 days; $> 0.5-1.0 \mu$ g/L:5 days; $> 1.0 \mu$ g/L:7 days). Physician follow-up is recommended.

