For subjects that we have been unable to reach to complete 30 day interviews via phone call, we will send a letter informing the subject that we have attempted to reach them without success. This letter will include a toll-free number that subjects may call in order to schedule or complete their interview. Alternatively, we will also provide a paper version of the interview questions for those subjects that prefer to complete via paper. Subjects will be provided with a prepaid envelope to send back completed paper interviews. Subjects may receive an email message reminder for the interview that will include a link to a Qualtrics version of the survey that is identical to the paper version. Subjects who have agreed to receive text messages may also be prompted to complete the survey via text messaging.

In the event that the participant is hospitalized between ProACT study enrollment and Day 30 at a facility different from the enrolling site, a medical release will be requested for feasibility of long-term follow-up to ascertain clinical events related to the study (Appendix 10).

iv. OUTCOMES

Our **primary outcome** is total antibiotic exposure, defined as the total number of antibiotic-days by Day 30. We define an antibiotic-day as each day a participant receives any oral or intravenous antibiotics, excluding antibiotics given for non-infectious indications (e.g. neomycin for hepatic encephalopathy) and antivirals. Secondary outcomes include the rate of antibiotic initiation by the initial ED clinician.

Our **primary safety outcome** is a combined endpoint of adverse outcomes that could be attributable to withholding antibiotics in LRTI, that occur by study Day 30, as below. Our combined endpoint captures the components of the treatment failure endpoint used in a recent study of 80,000 COPD patients (death, mechanical ventilation, readmission).²² We assume no patient discharged from ED has met primary safety outcome endpoint at time of discharge (death, organ failure, empyema); post-discharge events are captured in follow-up. Secondary outcomes include vital status at Day 90 and 1 Year, as determined by National Death Index (NDI) query.

Measurable adverse events for primary safety outcome:

- i. death
- ii. septic shock (vasopressor use for > 1h)

- iii. mechanical ventilation (via endotracheal tube)
- iv. renal failure (KDIGO-3)
- v. lung abscess/empyema
- vi. development of pneumonia in non-pneumonia LRTI

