ProHOSP estimated a maximum combined adverse outcome rate of 20% (actual – 17%) and set their non-inferiority margin as an absolute difference of 7.5%. In addition, a multicenter study of CAP (GenIMS), ~11% experienced our combined endpoint (6% death by Day 30, 5% septic shock, 7% mechanical ventilation, 10% renal failure). Similarly, a recent 80,000 COPD patient study reported 10.6% met a combined endpoint of death, mechanical ventilation, and readmission.²² We have therefore chosen an estimated combined adverse outcome rate of 11%. We also have set a narrower non-inferiority margin of 4.5%, approximately half that of ProHOSP's, to provide a higher degree of safety evaluation. **A sample size of 1514 patients provides at least 80% power to demonstrate that procalcitonin guideline implementation does not increase overall adverse outcomes by more than 4.5%, if the true difference between arms is zero.** This sample size also accounts for an approximately 10% lost to follow-up rate. Thus, we are well-powered to test safety.

vi. RECRUITMENT AND CONSENT

Each site will follow their IRB's guidelines regarding HIPAA authorization and informed consent (including those guiding the use of genetic material).

Patients will be screened for in the ED by the ProACT site study team. The ED clinical team will obtain potential participant or legally authorized representative (LAR)/proxy agreement verbally to be approached by the ProACT study representative to participate.

This will avoid “cold calling” coercion that could occur if direct contact by research team members was the initial method of assessing willingness to enroll.

Trained ProACT study team members will then discuss the trial with the patient or LAR/proxy, and explain the goals, procedures, and risks associated with the study. If patient or LAR/proxy agrees to participate, written authorization and consent will be obtained.

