Hospital follow-up	
 
• Antibiotics prescribed – name, dose, route, days
 
• Therapeutics and diagnostics – mechanical ventilation, steroids, bronchodilators, diuretics, radiologic tests
 
• Adverse outcomes – vasopressors/mechanical ventilation/new renal replacement therapy ever used, highest recorded creatinine, lung abscess/empyema, pneumonia diagnosed after enrollment (for non-CAP LRTI), date of discharge (length of stay), ICU admission
 
• Clinically obtained microbiology results
 
• Disposition – home, nursing home, rehabilitation facility, etc.
 
• 15-day and 30-day follow-up
 
• We used a structured interview process for vital status, antibiotic days, repeat ED visits/hospital admissions and reason, and quality of life.
 

Post-discharge survival	
 
• We are collecting 90-day and 1-year mortality data through a National Death Index (NDI) search or, for more recently enrolled subjects, by direct contact with the patient or their listed contacts. For NDI, there is a 2-year time lag before these data are available, so for patients enrolled near the end of the trial, we will perform primary analyses before their 1-year follow-up data are available, and a shorter follow-up will be handled with censoring.
 

[figure not shown]

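### As written, the renal component of the safety composite can be met by a creatinine already high on arrival, which dilutes the noninferiority comparison slightly and in the unsafe direction

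*SAP*

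**What the plan says.** The SAP (II. Measures, Primary outcomes) gives three alternative ways to meet renal failure: "new renal replacement therapy, tripling of baseline creatinine, or serum creatinine" of at least 4.0 mg/dL. The composite is assembled by "combining outcome occurrences from ED or hospital admission to discharge, with outcome occurrences from discharge to Day 30". SAP Table 1 lists "highest recorded creatinine" among the adverse-outcome variables in the hospital follow-up row.

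The Protocol (2.A.iii, Study interventions and procedures) sets a different origin: "time zero is at randomization and Day 1 is defined as time of enrollment through 11:59PM of the same day". The same section says that all creatinine results are collected. The exclusion criteria (2.A.ii) remove chronic dialysis, but no level of creatinine and no acute kidney injury.

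The only statement about events present early is in Protocol 2.A.iv: "We assume no patient discharged from ED has met primary safety outcome endpoint at time of discharge". It says nothing about patients who are admitted.

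**The concern.** In the renal definition, the word new qualifies replacement therapy only. The 4.0 mg/dL limb needs no change after arrival. The tripling limb depends on a baseline that neither document defines. Taken literally, with counting from ED or hospital admission, the rule scores renal failure present on arrival as a safety event.

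That cannot be an effect of withholding antibiotics, which is what the composite is meant to capture. Because these cases are settled before allocation, randomization spreads them evenly. They pull the risk difference toward zero, and in a noninferiority test this makes a real excess easier to miss. The SAP is alert to bias toward no difference for H2, but its per-protocol and CACE analyses address compliance and leave this untouched.

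The other non-fatal components are better guarded. Current vasopressor use, endotracheal ventilation and known abscess or empyema are exclusions. Pneumonia counts only in patients enrolled without it, and hospitalization must come later. The renal gap therefore looks like an oversight. The Protocol itself lists a related weakness of ProHOSP: "Their combined endpoint included an adverse outcome already potentially present at enrollment".

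**Working it through.** **Inputs.** Usual-care composite rate 11%, margin 4.5 points, loss to follow-up 10%, planned 757 per arm, later total 1,664 (SAP, Power and sample size). Final H2 critical value 1.71 (SAP Table 2). Final rule: upper limit of a two-sided 95% interval below 4.5%, so 1.96 (SAP, Analysis of primary outcomes). The prevalent share q is not in the documents; 1–5% is an assumption.

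**The plan's own figure.** 757 × 0.9 = 681 evaluable per arm. A simulation of the three looks with the Table 2 efficacy and futility boundaries gives 80.7% power, so 1,514 with at least 80% power reproduces. The sample-size arithmetic is not in error.

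**Dilution.** Let q be the fraction already meeting the criterion, equal in both arms.

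- Observed rate = q + (1−q) × incident rate.
- Observed difference = (1−q) × incident difference.
- At a true incident excess of 4.5 points: 0.99 × 4.5 = 4.46, 0.97 × 4.5 = 4.37, 0.95 × 4.5 = 4.28.

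**Case A: q adds to an 11% incident rate.** 1,664 / 2 × 0.9 = 749 per arm. p0 = q + (1−q) × 0.11 and p1 = q + (1−q) × 0.155.

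- Power at zero difference = Φ(0.045/SE − c), with SE = √(2p0(1−p0)/749).
- Error at the margin = Φ((0.045 − (p1−p0))/SE − c), with SE = √((p0(1−p0) + p1(1−p1))/749).

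Example, power at q = 3%: p0 = 0.1367, SE = 0.01775, 0.045/0.01775 − 1.71 = 0.825, Φ = 79.5%. Example, error at q = 5%: p0 = 0.1545, p1 = 0.1972, SE = 0.0196, 0.00225/0.0196 − 1.71 = −1.595, Φ = 5.5%.

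| q | Power (c = 1.71) | Error (c = 1.71) | Error (c = 1.96) |
|---|---|---|---|
| 0 | 85.8% | 4.4% | 2.5% |
| 1% | 83.7% | 4.6% | 2.7% |
| 3% | 79.5% | 5.1% | 3.0% |
| 5% | 75.8% | 5.5% | 3.3% |

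These are single-look approximations. In simulation over all three looks with q = 0, error is 4.4% with binding futility and 4.8% without.

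**Case B: q lies inside the 11%.** The observed rate is unchanged, so power at zero difference stays at 85.8%. The incident rate becomes (0.11−q)/(1−q), and the relative increase allowed by the margin is 0.045 divided by it.

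- q = 0: 11.0%, 41%
- q = 1%: 10.1%, 45%
- q = 3%: 8.2%, 55%
- q = 5%: 6.3%, 71%

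Error at the margin is nearly the same as in Case A. At q = 5% it is Φ(0.00225/0.0174 − c), which is 5.7% at 1.71 and 3.4% at 1.96.

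**The case against.** The strongest reply is that the effect is small and partly handled. Much of this stands. At q of 1% or less little changes. Error stays near its nominal level throughout, and under the 95% interval rule it stays below 5%. The SAP says that the pooled event rate was monitored blind with intent to adjust the sample size, so a composite rate raised by prevalent cases could have been seen there. That can protect power; it does not undo the dilution. Each component is also to be examined individually, which would show how much the renal one contributes.

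The label is KDIGO stage 3 and the SAP's reference is an acute kidney injury guideline, so it may be intended that a stable chronic value does not count. The wording does not say so. It would also not cover acute renal failure already present on arrival.

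Two stronger readings are tempting and are not supported:

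- *Renal failure dominates the planned event rate.* The Protocol's sample-size section reports "6% death by Day 30, 5% septic shock, 7% mechanical ventilation, 10% renal failure" within a composite of about 11%. Those figures come from a pneumonia cohort, and they overlap: 6 + 5 + 7 + 10 = 28. The second source for 11%, a COPD study, lists no renal component. ProACT also enrolls asthma, COPD, bronchitis and other LRTI. The 10% does not say how much renal failure was present on arrival.
- *The plan repeats exactly the flaw it criticizes in ProHOSP.* That criticism concerns ICU admission and rests partly on bed availability. ProACT leaves ICU admission out of its composite, so the parallel is partial.

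On timing, both interim analyses were complete by April 2017. Redefining a primary safety endpoint after them is more than an edit of wording.

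**Conclusion.** The concern holds as a defect of definition with a modest, one-directional effect. Applied literally, the stated rule counts renal failure present on arrival, and nothing in either document removes it. The bias favors noninferiority.

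The size depends wholly on q, for which the documents offer no figure, and on whether such cases add to the 11% or already form part of it. For q of 1–5% the absolute dilution is 0.04 to 0.22 points and error rises by about 0.2 to 1.3 percentage points at critical value 1.71. The larger consequences are alternatives: a loss of up to 10 points of power if the cases add to the 11%, or a looser margin in relative terms if they do not. The two should not be added together. A reader should not infer that such cases were observed, or that the trial's safety conclusion would be reversed.

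**What to change.** Before unblinding, amend the SAP as follows.

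1. Count every composite component from randomization, to agree with the Protocol's time zero.
2. Define baseline creatinine for the tripling limb.
3. Where the last creatinine at or before randomization is already 4.0 mg/dL or more, count the renal component only through new renal replacement therapy or tripling of that value. Moving the start of counting is not enough alone, because the same high value can be recorded again afterwards.
4. State how a missing enrollment creatinine is handled, since Table 1 lists only clinically obtained laboratory values.
5. Report the composite under both the current and the incident definition, with the number meeting the creatinine criterion at entry by arm.

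The interim analyses presumably used the current definition, so the sponsor may reasonably keep it as primary and prespecify the incident version as a sensitivity analysis.

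The cost is SAP text and derivation code; no new data are needed because all creatinine results are collected. The drawbacks are a slightly lower event count, some missing enrollment values and, if the incident version becomes primary, a final definition that differs from the interim one.
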